4.4 Data of Subjects with First Eye Treated in an Antecedent Study

For the 6 subjects who received timrepigene emparvovec treatment in their first eye in an antecedent study, the data from the antecedent study will not be included in the analyses presented in the Clinical Study Report (CSR).

4.5 Schedule of Analyses

At regular intervals during the study, the Data Monitoring Committee will review the progress and accrued study data and provide advice to the Sponsor on the efficacy and safety aspects of the study.

A final analysis will be conducted after all subjects complete the study.

4.6 Adjustment for Multiplicity

Not applicable for this study.

4.7 Subgroup Analysis

Demographic and baseline characteristics will be summarised by Surgery Site. The efficacy endpoints of BCVA will be summarised by the subgroups defined in [Table 1](#).

Table 1 Subgroups Defined at Baseline

	Values
Age 1	≤ 50 years old > 50 years old
Age 2	≤ 60 years old > 60 years old
Age 3	\leq median age $>$ median age
Race	White Non-white (American Indian or Alaska Native, Asian, Black or African American, Native Hawaiian or Other Pacific Islander)
Region	America Europe
Surgery Site	Each of the surgery sites
Surgery Window	Short [< 6 months], Medium [$6-12$ months] Long [>12 months] Overall

In addition, TEAE will also be summarized by Surgery Window (Short [< 6 months], Medium [$6-12$ months] and Long [>12 months]) and all surgery windows combined.

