7 INVESTIGATIONAL PLAN

7.1 Overall Study Design

This is a multi-centre, open-label, prospective, 2-period, bilateral interventional safety study of AAV2-REP1 in adult male subjects with genetically confirmed CHM. The study will consist of a Screening Period followed by 2 treatment periods (Period 1 and Period 2) with up to 9 visits per treatment period. A second baseline visit prior to surgery of SE2 (Period 2, Visit 1) may be required. A study schematic is presented in **Figure 1**.

Figure 1 Overall Study Schematic

During the Screening Period, subjects will be assessed for eligibility of both eyes. The Investigator will assign the order in which the eyes are treated (i.e., study eye 1 [SE1]-Period 1 and study eye 2 [SE2]-Period 2, respectively) with a number assigned to each eye. This will be done in collaboration with the subject; however, the worse eye will generally be selected for first treatment. Study eye selection and eligibility for surgery will then be confirmed collectively by the Patient Eligibility Review Committee, which includes the Investigator, a consulting surgeon, and the Sponsor (see the Patient Eligibility Review Plan). The estimated target interval between the surgical procedures of SE1 and SE2 will be determined at the Screening Visit.

Each study eye will be followed for at least 12 months post-treatment, for up to 9 visits per treatment period: Visit 1 (Day 0, Injection Day Visit); Visit 2 (Day 1, post-operative follow-up visit); Visit 3 (Day 3 + 2 Days); Visit 4 (Day 7 -1/+2 Days); Visit 5 (Day 14 ± 3 Days); Visit 6 (Month 1 ± 7 Days); Visit 7 (Month 3 ± 14 Days); Visit 8 (Month 6 ± 14 Days) and Visit 9 (Month 12 ± 14 Days; end of study visit).

At Period 1, Visit 1 (Day 0, Injection Day Visit for SE1), subjects will undergo a vitrectomy with retinal detachment and receive a sub-retinal injection of AAV2-REP1 in SE1. Visits 2-9 will then be conducted according to the Schedule of Study Procedures, unless Period 2 commences during the time of follow-up for SE; in which case, the study visits will continue following the schedule for SE2. Ophthalmic assessments during Period 1, Visits 2-9 will be performed on both eyes.

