The interval between SE1 and SE2 treatment is expected to vary among subjects from weeks to many months. While the interval will be decided on a case-by-case basis, an effort will be made to schedule varying treatment intervals in order to better characterise the immunological and safety profile of sequential treatment administration. Thus, approximately 20 subjects each will be treated with a short- (<6 month), medium- (6-12 months), or long- (>12 month) surgery window between treatment of the first and second

eye. Because the timing of the second surgery visit (Period 2, Visit 1) will vary among subjects, the duration of study Period 1 will also be variable.

The post-operative outcome and visual function of SE1 will inform the scheduling of Period 2. Signs of post-operative inflammation or other post-operative sequelae, as judged by the Investigator, should be resolved in SE1 for the subject to continue to Period 2. After comprehensive evaluation of all safety assessments and visual functional tests of SE1 and SE2, the Investigator will determine the eligibility of the subject and decide the appropriate time to schedule SE2, Visit 1.

All baseline ophthalmic assessments must be conducted within 10 weeks prior to SE2 surgery (Period 2, Visit 1). If these assessments are not available within the required timeframe, a Baseline Visit must be added to collect current baseline data on SE2. Study eye selection and eligibility for surgery will then be confirmed collectively by the Patient Eligibility Review Committee, which includes the Investigator, a consulting surgeon, and the Sponsor (see the Patient Eligibility Review Plan). If, at that time, BCVA in SE2 is <34 ETDRS letters, surgery may be performed when, in the opinion of the Patient Eligibility Review Committee: 1) the subject is found eligible by all other inclusion and exclusion criteria, and 2) the subject is considered an appropriate candidate who has potentially modifiable disease.

At Period 2, Visit 1 (Day 0, Injection Day Visit for SE2) subjects will undergo a vitrectomy with retinal detachment and sub-retinal injection of AAV2-REP1 in the contralateral, untreated eye (SE2). Post-treatment, subjects will no longer follow the Period 1 visit schedule, but will instead attend Period 2, Visits 2-9 according to the Schedule of Study Procedures. Ophthalmic assessments scheduled for Period 2, Visits 2-9 will be performed on both eyes.

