3.1 Discussion of Study Design

This is a Phase 2, multi-centre, open-label, prospective, 2-period, bilateral interventional safety study of timrepigene emparvovec in adult male subjects with genetically confirmed CHM.

The study will consist of a Screening Period followed by 2 treatment periods (Period 1 and Period 2) with up to 9 visits per treatment period. A second baseline visit prior to surgery of Study Eye 2 (SE2) (Period 2, Visit 1) may be required. A study schematic is presented in [Figure 1](#).

Figure 1 Overall Study Schematic

During the Screening Period, subjects will be assessed for eligibility of both eyes. The investigator will assign the order in which the eyes are treated (i.e., study eye 1 [SE1] period 1 and study eye 2 [SE2] period 2, respectively) with a number assigned to each eye. This will be done in collaboration with the subject; however, the worse eye will generally be selected for first treatment. The estimated target interval between the surgical procedures of SE1 and SE2 will be determined at the Screening Visit.

Each study eye will be followed for at least 12 months post-treatment, for up to 9 visits per treatment period: Visit 1 (Day 0, Injection Day Visit); Visit 2 (Day 1, post-operative follow up visit); Visit 3 (Day 3 + 2 Days); Visit 4 (Day 7 -1/+2 Days); Visit 5 (Day 14 ± 3 Days); Visit 6 (Month 1 ± 7 Days); Visit 7 (Month 3 ± 14 Days); Visit 8 (Month 6 ± 14 Days) and Visit 9 (Month 12 ± 14 Days).

The interval between SE1 and SE2 treatment is expected to vary among subjects from weeks to many months. While the interval will be decided on a case-by-case basis, an effort will be made to schedule varying treatment intervals in order to better characterise the immunological and safety profile of sequential treatment administration. Thus, approximately 20 subjects each will be treated with a short- (<6 month), medium- (6-12 months), or long- (>12 month) surgery window between treatment of the first and second eye. Because the timing of the second surgery visit (Period 2, Visit 1) will vary among subjects, the duration of study Period 1 will also be variable.

All baseline ophthalmic assessments must be conducted within 3 months prior to SE2 surgery (Period 2, Visit 1). If these assessments are not available within the required timeframe, a Baseline Visit must be added to collect current baseline data on SE2. If, at that time, BCVA in SE2 is <34 ETDRS letters, surgery may be performed when, in the opinion of the

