investigator and after consultation with the sponsor: 1) the subject is found eligible by all other inclusion and exclusion criteria, and 2) the subject is considered an appropriate candidate who has potentially modifiable disease.

The post-operative outcome and visual function of SE1 will inform the scheduling of Period 2. Signs of post-operative inflammation or other post-operative sequelae, as judged by the investigator, should be resolved in SE1 for the subject to continue to Period 2. After comprehensive evaluation of all safety assessments and visual functional tests of SE1 and SE2, the Investigator will determine the eligibility of the subject and decide the appropriate time to schedule SE2, Visit 1.

Subjects who develop cataracts may undergo cataract surgery if deemed clinically necessary. If cataract surgery is performed, it should be carried out at least 4 weeks before Month 12 (Visit 9) for the respective eye. The cataract surgery timing must be discussed with the medical monitor prior to the procedure.

Subjects Previously Treated with Timrepigene Emparvovec

Subjects who have previously participated in a clinical trial of AAV2-REP1 for the treatment of CHM and have received AAV2-REP1 in one eye may be eligible for participation in this study. In these cases, only the subject's untreated eye will be assessed for eligibility. Following the Screening Visit and determination of eligibility, the subject will move directly into Period 2 for treatment of SE2.

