4.17.10 Adverse Events

Treatment Emergent Adverse Events (TEAEs) are defined as AEs starting on or after the day of the first surgery. AEs reported in subjects who received timrepigene emparvovec treatment in their first eye in an antecedent study will be considered as TEAEs. Where an AE start date is partially or fully missing, and it is unclear as to whether the AE is treatment emergent, it will be assumed that it is. Summary tables will include TEAEs only. TEAEs will be summarised by eye (for ocular events), by period, and overall. Each by-period summary table will be repeated by surgery window instead.

The number and percentage of subjects reporting any event, any non-ocular event, any ocular event, any ocular event in SE1 and any ocular event in SE2 will be summarised. Percentage will be calculated based on the number of subjects in the corresponding period or surgery window or overall. The 95% CI will be calculated using the Clopper-Pearson method.

Overall summary table of TEAE by period (or by surgery window) will be provided for the following categories:

- Number and percentage of subjects with a TEAE
- Number and percentage of subjects with a serious TEAE
- Number and percentage of subjects with a Treatment-related (study drug or study procedure) TEAE
- Number and percentage of subjects with a Treatment-related (study drug or study procedure) serious TEAE
- Number and percentage of subjects with a TEAE leading to death
- Number and percentage of subjects who discontinued due to a TEAE
- Number and percentage of subjects with a TEAE by severity
- Number and percentage of subjects with a TEAE by outcome
- Number and percentage of subjects with a TEAE by action taken

Adverse events will be summarized by period (or by surgery window), and overall. The following summaries of TEAEs will be provided:

- TEAEs by SOC and PT
- TEAEs by PT with percentage $\geq 5\%$
- Treatment-related (study drug or study procedure) TEAEs by SOC and PT
- Study procedure-related TEAEs by SOC and PT
- Study drug-related TEAEs by SOC and PT
- TEAEs by SOC, PT, and maximum severity (missing severity, if any, will be counted as severe).
- Serious TEAEs by SOC and PT
- Treatment-related (study drug or study procedure) serious TEAEs by SOC and PT
- Study procedure-related serious TEAEs by SOC and PT
- Study drug-related serious TEAEs by SOC and PT
- TEAEs leading to death by SOC and PT
- TEAEs reported by subjects who discontinued due to SAE by SOC and PT

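### Surgery Window is listed as a baseline subgroup, but the interval is known only at SE2 surgery and depends partly on SE1's recovery, so SE1 and pooled adverse-event results by window are open to bias

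*SAP*

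**What the plan says.** Table 1 in SAP 4.7, titled "Subgroups Defined at Baseline", includes Surgery Window with the values short (under 6 months), medium (6-12 months), long (over 12 months) and overall. SAP 4.16.1 summarises all BCVA endpoints, for both eyes and both periods, by these subgroups. SAP 4.7 adds that "TEAE will also be summarized by Surgery Window". SAP 4.17.10 counts treatment-emergent events from the first surgery and says "Each by-period summary table will be repeated by surgery window instead", with this denominator rule: "Percentage will be calculated based on the number of subjects in the corresponding period or surgery window or overall". Fixation stability (SAP 4.16.4) and the immunogenicity analyses (SAP 4.17.11.3 and 4.17.11.4) also use the window.

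SAP 3.1 describes the window as a time between two treatments: "long- (>12 month) surgery window between treatment of the first and second eye". On how it arises, Protocol 7.1 says "The estimated target interval between the surgical procedures of SE1 and SE2 will be determined at the Screening Visit" and also "The post-operative outcome and visual function of SE1 will inform the scheduling of Period 2". SAP 3.1 adds that inflammation or other sequelae "should be resolved in SE1 for the subject to continue to Period 2".

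Protocol 8.3 provides that after certain poor SE1 outcomes SE2 should not, or may not, be treated while Period 1 follow-up continues. Under SAP 4.1 these subjects stay in the All Treated Subjects set. The SAP does not say whether the window is the target or the actual interval, where subjects without SE2 surgery go, or whether the overall column includes them.

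**The concern.** Age, race, region and site are fixed before the first surgery. The actual interval is not: it becomes known only at SE2 surgery, after SE1's result has had a chance to move it. Tabulating SE1 BCVA or SE1 adverse events by actual window therefore groups results by a variable that those results helped to determine. If a complication in SE1 postpones SE2, complicated first eyes collect in the longer windows and uncomplicated ones in the shorter, even when the interval does nothing.

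Two further features matter. Adverse events pooled from first surgery are observed for longer when the gap is longer, yet the percentages use subjects as denominator. And subjects whose SE1 did badly enough that SE2 was withheld belong to no window.

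The stake is interpretation. Protocol 7.1 varies the interval so as to characterise the immunological and safety profile of sequential treatment, so readers will look across the three columns.

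**Working it through.** **Inputs from the documents.** About 60 subjects, about 20 per window (Protocol 7.1 and 13.1; SAP 3.1 and 3.6). Period 1 ends the day before SE2 surgery (SAP 4.3). Adverse events are collected through Period 2, Month 12 (Protocol 11.1.2). Six subjects treated first in an antecedent study contribute Period 2 only (SAP 4.3). The documents give no SE1 complication rate, frequency or length of delay, share never treated in SE2, between-eye correlation or event rate. All such values below are assumptions.

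**1. The plan's own figures.** 3 × 20 = 60 subjects and 60 × 2 = 120 eyes, as stated. The 120 requires every subject to have both eyes treated.

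**2. Effect of delay on SE1 event rates, no true window effect.** Let p be the SE1 inflammation rate (unrelated to the planned window), u the share of affected subjects never treated in SE2, and d the share of affected, still-treated subjects who slip one class. Planned windows are equal, and long cannot slip further. With m = p(1 − u):

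- Short: m(1 − d) / [(1 − p) + m(1 − d)]
- Medium: m / [(1 − p) + m]
- Long: m(1 + d) / [(1 − p) + m(1 + d)]

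For p = 0.20 and u = 0.20, m = 0.16:

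| d | Short | Medium | Long |
|---|---|---|---|
| 0 | 0.16/0.96 = 16.7% | 16.7% | 16.7% |
| 0.10 | 0.144/0.944 = 15.3% | 16.7% | 0.176/0.976 = 18.0% |
| 0.25 | 0.12/0.92 = 13.0% | 16.7% | 0.20/1.00 = 20.0% |
| 0.50 | 0.08/0.88 = 9.1% | 16.7% | 0.24/1.04 = 23.1% |

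By planned window, keeping everyone, the rate is 20% in each. Subjects with no window are pu = 4%, or 2.4 of 60. At d = 0.50, p = 0.10 gives 4% / 8% / 12% and p = 0.30 gives 15% / 26% / 34%.

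**3. The same mechanism for BCVA.** A simulation of 1,000,000 subjects with no window effect assumed a 15% SE1 complication risk, a mean 15-letter loss when complicated, SD 6, delays of 3-9 months, 30% of complicated cases never treated in SE2, and between-eye correlation 0.5. Percentages with a loss of at least 15 letters:

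| Outcome and grouping | Short | Medium | Long |
|---|---|---|---|
| SE1, actual window | 1.0% | 5.6% | 10.5% |
| SE1, target window, everyone kept | 8.1% | 8.0% | 8.0% |
| SE1, actual window, nobody delayed | 6.0% | 6.1% | 6.1% |
| SE2, actual window | 6.1% | 7.5% | 8.7% |
| SE2, actual window, correlation 0 | 7.9% | 8.0% | 8.1% |

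With complication risks of 5% and 30%, SE1 short against long is 0.8% against 4.0% and 1.6% against 19.2%. Subjects never treated in SE2 number 0.15 × 0.30 × 60 = 2.7 in the base case and carry 28% of the large SE1 losses.

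**4. Unequal time at risk for pooled adverse events.** At-risk time is the gap plus 12 months. Take gaps of 3 and 15 months and the same constant rate of 0.5 first events per year:

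- Short: 1 − exp(−0.5 × 15/12) = 46.5%
- Long: 1 − exp(−0.5 × 27/12) = 67.5%

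At 0.1 per year the pair is 11.8% and 20.1%; at 1.0 per year, 71.3% and 89.5%. This needs no delay at all. It does not apply to the six antecedent-study subjects, who are observed in Period 2 only.

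**5. Precision.** With 20 per window, 2/20 has a Clopper-Pearson 95% interval of 1.2% to 31.7%, and 5/20 of 8.7% to 49.1%.

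**The case against.** The SAP never says that the actual interval is the grouping variable. A target interval is set at screening, which would fit the table's title. SAP 4.2 rules out formal comparison. Subjects without SE2 surgery stay in the analysis set and in every by-period table, and the window tables only repeat those. BCVA is shown by eye and period, and the ocular inflammation and reduced-acuity tables by eye with onset split at 30 days, so SE1 and SE2 can be read apart. Intervals at 20 per window are wide.

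Much of this limits the point but does not remove it. A time between two treatments is most naturally the actual one. Descriptive columns are still compared, and a confidence interval does not show this kind of bias.

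A reader might infer more than the documents support:

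- *That all window comparisons are biased, or that longer intervals must look less safe.* For outcomes after SE2 surgery the window is already fixed and Period 2 has its own baseline. What remains is possible confounding by SE1 recovery, which was small in step 3 and essentially absent at zero between-eye correlation. For SE1, the gradient from delay disappears if nobody is delayed.
- *That leaving out subjects never treated in SE2 distorts the differences between windows.* On its own it lowers all three about equally (6.0-6.1% against 8.0%). It understates harm rather than tilting the comparison. The SAP also does not settle whether they are left out of the overall column.
- *That the regulator wanted SE1 safety judged by window.* The change summary for protocol version 3.0 gives the purpose as a broad safety profile across intervals, and Protocol 7.2 stresses the immunological profile. Neither asks for that.
- *That the target interval is on file.* The protocol says it is determined; neither the screening list nor the schedule of procedures shows it being recorded.

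**Conclusion.** The point holds in limited form. The actual window is not a baseline characteristic, and some treated subjects have none. If it is the grouping variable, SE1 and Period 1 BCVA and adverse events pooled from first surgery are open to bias by window, through conditioning on a later event and, for pooled events, through longer time at risk. Those columns cannot be read as an effect of the interval.

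The size cannot be derived from the documents. Under the assumptions in step 2, the spread between short and long runs from zero to 14 percentage points (23.1 − 9.1) at 20% inflammation, driven by the assumed share delayed. The follow-up artefact in step 4 depends on the assumed event rate and gaps.

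**What to change.** - Retitle Table 1, or move Surgery Window out of it, and state that it is the actual interval between SE1 and SE2 surgery. State the rule for the six antecedent-study subjects.
- Use the actual window only for events and changes from SE2 surgery onward, over the common 12 months of follow-up after that surgery. Showing SE1 status alongside would let readers judge the remaining confounding.
- For SE1 and Period 1 results, group by the screening target interval if it was captured. If not, do not present them by window, or present them over a fixed interval after SE1 surgery with a caveat. Target grouping does not cure unequal follow-up, so Period 1 event percentages need a fixed interval or person-time rates in either case.
- Add an SE2-not-treated column with reasons, and include those subjects in the overall column.

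The cost is SAP wording, one extra classification and some table shells. The sponsor must confirm that the target interval is in the database. The change concerns analysis and reporting only and leaves the scheduling of surgery untouched.

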4.8 Handling of Missing Values

The number, pattern and timing of missing data will be examined along with the reasons for withdrawal or for missing data.

The safety analyses will be performed using the ‘observed case’ method. In the efficacy analysis, observed case method will be applied as main analysis for categorical and continuous endpoints. The following supportive analysis will be performed for BCVA related endpoints: both categorical endpoints and continuous endpoints will be imputed using the ‘Last Observation Carried Forward’ (LOCF) method with the last available measurement prior to missing (see details in [Section 4.16.1](#)).

4.9 Statistical Analyses Handling of Data Impacted by COVID-19

Currently there is an outbreak of respiratory disease caused by a novel coronavirus (COVID-19). In terms of the statistical analysis, the impact of the COVID-19 pandemic on the GEMINI study will be evaluated by summarizing the number and percentage of subjects, by treatment and overall:

- Who died during the study due to COVID-19;
- Who withdrew from the study due to COVID-19;

The information for subjects who died during the study or withdrew from the study due to COVID-19 will be recorded in the eCRF.

4.10 Disposition of Subjects

The number of subjects who sign Informed Consent, who receive study treatment, who complete the study and the reasons for any premature discontinuation from the study will be presented. The number of subjects included in the All Treated Subjects analysis set and the Immunogenicity analysis set will also be presented. For each study visit, the number of subjects who attend the visit will be summarised.

